8.2.3. Reporting and Follow-up of Pregnancies

All pregnancies in female participants and female partners of male participants receiving at least 1 dose of study drug will be reported if they occur anytime from first dose to 4 months after the last dose of study drug. The Investigator is responsible for informing MyoKardia within 24 hours of knowledge of the pregnancy, even if no AE has occurred, per the reporting guidelines in [Section 10.1.4](#). The participant will be asked to provide information on the outcome of the pregnancy through 6 months after birth or details of premature termination. Spontaneous miscarriage and congenital abnormalities will be reported as SAEs.

9. STUDY ASSESSMENTS AND PROCEDURES

The Investigator is responsible for ensuring that all staff involved in the study are familiar and comply with the content of this section.

The following describes the study procedures to be performed during the study. Additional details are provided in [Table 2](#). When several assessments are to be conducted at the same time point, the preferred order of assessments is ECG, vital signs, PK, and then TTE. The order of assessments may vary slightly at specific time points (eg, 1-hour postdose) to facilitate the most contemporaneous performance of the required assessments. Unscheduled or additional safety assessments may be performed if necessary in the opinion of the Investigator.

For assessments that require the participants to be in a semi-recumbent or supine position, assessments should be conducted with participants in the same position at all time points.

9.1. Efficacy and Pharmacodynamic Assessments

9.1.1. Echocardiography

Details are provided in the Study Reference Manual. Echocardiography should be performed prior to dosing. Echocardiograms will be site-read and not blinded to the Investigator or the site. All echocardiography data will be sent to the interactive response system (IXRS) for LVEF stopping criterion (LVEF < 50% by local site-read). Echocardiograms will also be sent to a central imaging laboratory for possible future assessment. If necessary, contrast may be administered to ensure that high quality echocardiogram images are obtained.

9.1.1.1. Resting Transthoracic Echocardiography

Resting TTE will be assessed throughout the study, as indicated in [Table 2](#) and [Table 3](#). Instantaneous peak LVOT gradient at rest and provoked peak LVOT gradient (Valsalva maneuver) will be assessed. LVEF and other parameters will be obtained (see Study Reference Manual).

Resting TTE should be performed prior to stress echocardiography.

9.1.1.2. Stress Echocardiography

Participants will undergo a standard symptom-limited exercise test (stress echocardiography), after a 4-hour fast, at the visits indicated in [Table 2](#) and [Table 3](#). The instantaneous peak LVOT gradient will be assessed immediately post-exercise by TTE. Any concomitant medication or

standard therapies for the treatment of HCM should be taken, as prescribed, on the day of the exercise test.

9.1.2. New York Heart Association Functional Class

The NYHA Functional Classification of heart failure assigns participants to 1 of 4 categories based on the participant’s symptoms (Table 4). Heart failure classification will be assessed at every clinical site study visit indicated in Table 2.

Table 4 New York Heart Association Functional Classification of Heart Failure

Class	Patient Symptoms
I	No limitation of physical activity. Ordinary physical activity does not cause undue fatigue, palpitation, dyspnea (shortness of breath).
II	Slight limitation of physical activity. Comfortable at rest. Ordinary physical activity results in fatigue, palpitation, dyspnea (shortness of breath).
III	Marked limitation of physical activity. Comfortable at rest. Less than ordinary activity causes fatigue, palpitation, or dyspnea.
IV	Unable to carry on any physical activity without discomfort. Symptoms of heart failure at rest. If any physical activity is undertaken, discomfort increases.

Source: [American Heart Association’s Classes of Heart Failure, 2015](#).

9.1.3. Kansas City Cardiomyopathy Questionnaire

The KCCQ is a self-administered 23-item questionnaire that quantifies physical limitation, symptoms, quality of life (QoL), social interference, and self-efficacy (Green et al, 2000). The total symptom score is derived from the symptom frequency and symptom burden scores. The clinical summary score is derived from the physical limitation and total symptom scores. The overall summary score is derived from the physical limitation, symptom, QoL, and social interference domains. Scores range from 0 to 100, with higher scores reflecting better health status. The KCCQ will be administered to participants as indicated in Table 2.

9.2. Pharmacokinetic Assessments

9.2.1. Pharmacokinetic Assessments

Blood samples will be collected for mavacamten plasma concentration assessments throughout the treatment period as indicated in Table 2. At all time points, a blood draw for drug concentration must be obtained prior to dosing.

9.2.2. NT-proBNP

Blood samples will be collected for NT-proBNP concentrations throughout the study, as indicated in Table 2 and Table 3. Unscheduled or additional blood samples may be collected if appropriate in the opinion of the Investigator and/or Sponsor. At all visits in which a stress echocardiography is performed, the blood draw for NT-proBNP will occur prior to stress echocardiography.

9.3. Safety Assessments

Safety will be assessed throughout the study. Safety assessments include medical history, physical examinations, ECGs, vital signs, observed and participant-reported AEs, and safety laboratory results. Any abnormal findings judged by the Investigator to be clinically important will be recorded as an AE.

9.3.1. Medical History

A complete medical history will be recorded at the Screening visit, which will include evaluation (past or present) of the following: general, head and neck, eyes, ears, nose, throat, chest/respiratory, heart/cardiovascular, gastrointestinal/liver, gynecological/urogenital, musculoskeletal/extremities, skin, neurological/psychiatric, endocrine/metabolic, hematologic/lymphatic, allergies/drug sensitivities, past surgeries, substance abuse, or any other diseases or disorders as well as participation in clinical studies (study medication and/or device or other therapy). Specific history related to a participant's HCM diagnosis will also be collected.

9.3.2. Physical Examination

At the Screening visit, a complete physical examination will be conducted including a neurological examination (gross motor and deep tendon reflexes), height and weight, and assessment of the following: general appearance, skin, head and neck, mouth, lymph nodes, thyroid, abdomen, musculoskeletal, cardiovascular, neurological, and respiratory systems. At all other visits, an abbreviated cardiopulmonary physical examination will be conducted, with other systems assessed as directed by interval history; weight will also be recorded.

Height (cm) and body weight (kg) will be measured at Screening, and body mass index (kg/m^2) will be calculated. Participants will be required to remove their shoes and wear clothing as specified by the clinical site. Weight will also be collected at all subsequent onsite visits.

9.3.3. 12-lead ECG

Twelve-lead ECG evaluations will be performed after 10 minutes of rest throughout the study, as indicated in [Table 2](#) and [Table 3](#). All ECG data will be sent to a central cardiac laboratory.

On Day 1, ECG will be performed predose. At all other visits, ECGs may be obtained at any time.

The Investigator will judge the overall interpretation as normal or abnormal with clinical significance. The Investigator will review the ECG and correlate abnormal findings with any other clinical findings, participant's medical history, and laboratory data to determine the clinical importance of the finding.

The Investigator may add extra 12-lead ECG safety assessments if there are any abnormal findings or if the Investigator considers it is required for any other safety reason. These assessments should be recorded as an unscheduled assessment.

9.3.4. Vital Signs

Vital signs are to be assessed throughout the study as indicated in [Table 2](#), including temperature, heart rate (HR), respiratory rate, and blood pressure (BP) after resting for at least

5 minutes. Vital signs will be obtained with the participant in the same position; BP will be taken via an automated recorder.

Vital signs will be taken prior to dosing. Refer to the Study Reference Manual for additional details.

9.3.5. Other Safety Assessments

Refer to [Section 10](#) for information on AE assessment and [Section 7.7.2](#) for concomitant therapy assessments.

Safety laboratory results will be assessed in an ongoing manner. A central safety laboratory will be used. Laboratory parameters are provided in [Appendix 1](#).

9.4. Participant Restrictions During this Study

The following restrictions apply for the specified times during the study period. If a participant does not comply with these restrictions or tests positive in any laboratory tests (eg, pregnancy), he or she may be excluded or withdrawn from the study.

- Starting at Screening, participants will be required to abstain from blood or plasma donation until 4 months after the final study visit
- Starting on Day 1 until the final follow-up visit, participants will be asked to abstain from grapefruit or grapefruit juice, Seville oranges, and quinine (eg, tonic water)
- Contraception requirements are discussed in [Section 8.2](#)

9.5. Study Procedures by Visit

Study procedures are presented by visit in [Table 2](#) and [Table 3](#). Every effort should be made to avoid protocol deviations.

At the Investigator's discretion, unscheduled visits may be conducted for the assessment of AEs, physical examinations, vital signs, laboratory tests, drug dispensing, ECGs, and/or TTEs. All information collected from unscheduled visits will be recorded on the eCRF and included in the clinical database.

9.6. Visit Scheduling

All visits should occur within the visit window (± 4 days for Week 4; ± 7 days for all remaining visits from Week 6 to Week 260/EOS). If an evaluation is missed, reschedule and perform it as close as possible to the original date.

10. EVALUATION, RECORDING, AND REPORTING OF ADVERSE EVENTS, SERIOUS ADVERSE EVENTS, AND ADVERSE EVENTS OF SPECIAL INTEREST

Safety assessments will consist of monitoring and recording of AEs, including SAEs and adverse events of special interest (AESIs), performing protocol-specified safety laboratory assessments, measuring protocol-specified vital signs, and conducting other protocol-specified tests that are deemed critical to the safety evaluation of the study.

Hospitalization or procedural intervention for endpoint events (myectomy, septal ablation) will not be captured as SAEs, but will be recorded on specialized eCRFs.

10.1. Definitions of Pretreatment Adverse Events, Adverse Events, Serious Adverse Events, and Adverse Events of Special Interest

10.1.1. Pretreatment Adverse Events

A pretreatment adverse event (PTAE) is an AE that occurs in a participant who has signed informed consent to participate in a study but has not received any study drug. A PTAE may result from a protocol-mandated procedure (eg, phlebotomy, invasive procedure, such as biopsy) but does not necessarily have to have a causal relationship with study participation.

10.1.2. Adverse Events

- According to the International Council for Harmonisation (ICH) guideline for GCP, an AE is defined as any untoward medical occurrence in a clinical investigation participant administered a pharmaceutical product; it does not necessarily have to have a causal relationship with this treatment.
- An AE can therefore be any unfavorable and unintended sign (eg, tachycardia, enlarged liver, clinically important or abnormal laboratory finding), symptom (eg, nausea, chest pain), or evidence of disease activity temporally associated with the use of a study medication, whether or not related to the study medication.
- Each AE should be recorded as a single diagnosis. Accompanying signs (including abnormal laboratory values or ECG findings) or symptoms should not be recorded as additional AEs. If a diagnosis is unknown, signs or symptoms should be recorded appropriately as a PTAE or AE.
- Any new disease or exacerbation of an existing disease (eg, a worsening in the character, frequency, or severity of a known condition) is an AE except as described below:
 - Preexisting medical conditions (present at the time of signing of informed consent) are considered concurrent medical conditions and should not be recorded as PTAEs or AEs. However, if the participant experiences a worsening or complication of such a concurrent condition, the worsening or complication should be recorded appropriately as a PTAE (worsening or complication occurs before the first dose of study drug) or an AE (worsening or complication occurs after the first dose of study drug). Investigators should ensure that the event term recorded captures the change in the condition (eg, “worsening of ...”).
- Recurrence of an intermittent medical condition (eg, headache) not present prior to the first dose of study drug
- Any deterioration in a laboratory value or other clinical test (eg, ECG, X-ray) that is associated with symptoms or leads to a change in study treatment or concomitant treatment or discontinuation from study drug

The following additional points should be considered for PTAEs and AEs:

- Preplanned medical or surgeries or procedures
 - Preplanned surgeries or procedures that were scheduled prior to signing of informed consent are not considered PTAEs or AEs. However, if a planned procedure is performed early (eg, as an emergency) due to worsening of a preexisting condition, the worsening of the condition should be captured appropriately as a PTAE or AE.
- Hospitalization for elective surgeries or procedures
 - Elective procedures performed for which there is no change in the participant's medical condition should not be recorded as PTAEs or AEs.
 - A hospitalization that was planned prior to the study or was scheduled during the study when the elective surgery or procedure became necessary because of the expected normal progression of the disease should not be recorded as PTAEs and AEs.
- Insufficient clinical response (lack of efficacy)
 - Insufficient clinical response, lack of efficacy, or pharmacologic action should not be recorded as an AE. The Investigator must make the distinction between exacerbation of preexisting medical condition and lack of therapeutic efficacy.
- Overdose
 - Cases of overdose with any medication without manifested side effects are not considered PTAEs or AEs.

The following should not be recorded as PTAEs or AEs:

- Any clinically significant abnormal laboratory findings or other abnormal safety assessments that are associated with the disease/disorder being studied, unless judged by the Investigator to be more severe than expected for the participant's condition
- The disease/disorder being studied or expected progression, signs, or symptoms of the disease/disorder being studied, unless more severe than expected for the participant's condition
- Situations in which an untoward medical occurrence did not occur (social and/or convenience admission to a hospital)
- Anticipated day-to-day fluctuations of a preexisting disease or condition present or detected at the start of the study that do not worsen

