11.2. Study Endpoints

11.2.1. Safety Endpoints

- Frequency and severity of treatment-emergent AEs and SAEs
- Frequency of cardiovascular (CV) death
- Frequency of sudden death
- Frequency of CV hospitalization
- Frequency of heart failure due to systolic dysfunction, defined as a symptomatic LVEF < 50%
- Frequency of myocardial infarction
- Frequency of ventricular arrhythmias (ventricular tachycardia, ventricular fibrillation, ventricular flutter, torsade de pointe)
- Frequency of syncope
- Frequency of seizures
- Frequency of stroke
- Frequency of LVEF < 50% as measured by echocardiography
- QT and QTcF intervals over time

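### Section 10.1.2 keeps expected disease signs and unchanged preexisting conditions out of AE recording without exempting the Section 11.2.1 endpoints, so recording of non-serious syncope rests on investigator judgment

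*Combined protocol and SAP*

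**What the plan says.** All references are to the combined protocol and SAP.

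**Endpoints.** Section 11.2.1 lists "Frequency of syncope", ventricular arrhythmias of four named types, and "Frequency of CV hospitalization" among 12 safety endpoints. None is restricted to unexpected events.

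**AE exclusions.** The closing list of Section 10.1.2 says that the following are not AEs: "expected progression, signs, or symptoms of the disease/disorder being studied, unless more severe than expected for the participant's condition". It also removes "Any clinically significant abnormal laboratory findings or other abnormal safety assessments that are associated with the disease/disorder being studied", unless the investigator judges them more severe than expected. Expected day-to-day fluctuation of a condition present at study start is excluded when it does not worsen. Earlier in the section, conditions present at consent are not AEs unless they worsen or cause a complication. Recurrence appears as an AE in this form: "Recurrence of an intermittent medical condition (eg, headache) not present prior to the first dose of study drug".

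**General rule.** Section 9.3 states: "Any abnormal findings judged by the Investigator to be clinically important will be recorded as an AE".

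**Admissions.** Under Section 10.1.2, an admission "scheduled during the study when the elective surgery or procedure became necessary because of the expected normal progression of the disease" is not an AE. The opening of Section 10 sends septal-reduction admissions and procedures to specialized eCRFs and not to SAE reporting. Section 7.7.2 puts concomitant procedures on an eCRF.

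**The concern.** Long-term safety and tolerability is the primary objective (Section 3.1) of a single-arm, open-label study with no hypothesis test. The reported event frequencies are therefore the result, and no control arm under the same recording rule is available for comparison.

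Section 10.2.2 intends events to be documented whatever the investigator thinks about drug causality. Under Section 10.1.2, however, attributing an event to the disease can keep it off the AE page before causality is considered. Section 10.2.1 captures relatedness only for treatment-emergent AEs, so an excluded event would get no causality assessment. Two sites could both follow the protocol and still record the same event differently. The reported frequency of syncope would then partly reflect local views of what is usual for a participant.

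**Working it through.** The plan gives no figure to reproduce. The check sets the rules side by side.

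**1. Which endpoints are exposed.** Section 11.2.1 has 12 entries: TEAEs/SAEs, CV death, sudden death, CV hospitalization, systolic heart failure, myocardial infarction, ventricular arrhythmias, syncope, seizures, stroke, LVEF < 50%, and QT/QTcF. LVEF and QT/QTcF are measured directly. Three of the 12 are directly exposed: syncope and ventricular arrhythmias through the recording rule, and CV hospitalization through its missing definition. The overall TEAE count is affected only through the same events.

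**2. Event by event.**

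| Event after first dose | Rule that applies | Outcome |
|---|---|---|
| Syncope or arrhythmia that is life-threatening or leads to an unplanned admission | 10.1.3 | SAE |
| Syncope more frequent or more severe than before | 10.1.2, worsening | AE |
| ECG deterioration with symptoms or a treatment change | 10.1.2 | AE |
| First non-serious syncope, judged an expected sign of HCM | 10.1.2 exclusion against the 11.2.1 endpoint | Judgment |
| Repeat non-serious syncope, unchanged, in a participant with syncope before the first dose | 10.1.2: disease-sign exclusion, preexisting-condition rule, arguably the fluctuation rule; the recurrence item does not clearly apply | Can be left unrecorded |
| Non-serious ventricular arrhythmia judged expected | Same exclusions, but 1.3 names arrhythmia due to QT prolongation as a potential drug risk | Judgment; less likely to be excluded |

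The important-medical-event limb of Section 10.1.3 could also capture these events, but it is itself a judgment.

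**3. Section 9.3 against Section 10.1.2.** They collide on findings that are associated with the disease, clinically important, and no more severe than expected. Section 9.3 records them and Section 10.1.2 does not. No order of precedence is stated.

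**4. Other capture routes.** Syncope and ventricular arrhythmia are not AESIs (Section 10.1.4). The specialized eCRFs are named only for myectomy and septal ablation. Sections 11.3.8.1 to 11.3.8.5 name no separate source for syncope. All ECGs go to a central laboratory (9.3.3), and new ECG morphologies are summarized (11.3.8.2), but a resting ECG at a visit does not replace event recording between visits. Data collected at unscheduled visits go on the eCRF (9.5), which helps only if the event leads to such a visit. Detection is not the problem: AEs are marked in all 21 columns of Table 2 (6 from Screening to Week 12, plus 15 from Week 18 to Week 102 at six-week steps). However, Table 2 footnote e records changes after the first dose only if they meet the AE definition, which leads back to Section 10.1.2.

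**5. Scale.** One participant is 100/n percentage points: 100/20 = 5.0. If fewer than the permitted 20 enroll (assumed sizes), 100/15 = 6.7 and 100/10 = 10.0. This holds for any single miscount.

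As an illustration, assume a true participant-level risk p and a recorded share s of affected participants, neither of which is in the documents. The chance of at least one recorded case among 20 is 1 − (1 − p·s)^20:

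| p | s = 100% | s = 50% |
|---|---|---|
| 5% | 64.2% | 39.7% |
| 10% | 87.8% | 64.2% |
| 20% | 98.8% | 87.8% |

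**The case against.** The strongest reply is that the harm depends on a data flow nobody can see here. No text says that the listed endpoints are counted from the AE page, and septal reduction shows that the sponsor does use endpoint forms. A syncope or arrhythmia page may exist. This stands, and it limits the point to a risk. It does not remove the conflict in the protocol text.

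Second, leaving an unchanged baseline condition out of AE recording is a coherent choice, in line with the new-onset-or-worsening test for treatment emergence in Section 11.3.8.1. In the repeat-syncope example, the preexisting-condition rule alone gives that result. This also stands. It means that a fix lifting only the disease-related exclusions would not be enough. It does not explain how a frequency-of-syncope endpoint is to be counted when such an event is omitted.

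Third, the arrhythmia part is thin: serious and symptomatic cases are largely covered. This is accepted.

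Fourth, Section 9.3 is a general sentence and Section 10.1.2 is the detailed definition, so a reader could let the latter govern. That is reasonable, but the protocol does not say so.

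Stronger readings are tempting and not supported:

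- A reader might infer that the documents class syncope or arrhythmia as expected in HCM. They nowhere do; the matter is left open.
- A reader might infer that elective CV admissions have no stated status at all. Section 10.1.2 states that they are not AEs, the opening of Section 10 gives septal-reduction admissions their own forms, and Section 7.7.2 documents procedures. Only their status under the CV hospitalization endpoint is missing.
- A reader might infer that events have been undercounted. Nothing in the documents shows this.

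**Conclusion.** The point holds as an unresolved conflict between the AE recording rules and the safety endpoint list. In the available text, a non-serious syncope judged usual for the participant can be left unrecorded by a site that follows Section 10.1.2, although Section 11.2.1 lists syncope without restriction. The same is possible, but less likely, for a non-serious ventricular arrhythmia. The unstated place of elective and septal-reduction admissions under CV hospitalization is a separate and lesser gap.

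The size cannot be derived from the documents, and the figures above show scale only. The conclusion assumes that no eCRF page or manual instruction outside the available text already requires these events to be recorded regardless of expectedness. If one does, the remaining work is to align the protocol wording. The change is worth making because the affected events belong to the primary objective and the remedy is short. Confidence is medium.

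**What to change.** Add to Section 10.1.2:

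> The exclusions for expected progression, signs or symptoms, for disease-associated abnormal assessments, for unchanged preexisting conditions and for day-to-day fluctuations do not apply to syncope, ventricular arrhythmia or any other clinical event listed in Section 11.2.1 that occurs after the first dose. Such events are entered on the eCRF (AE or endpoint page) regardless of expectedness or attribution to HCM, and are SAEs only if Section 10.1.3 is met.

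State in Section 11.2.1 whether elective admissions and septal-reduction admissions count as CV hospitalization. Reconcile Section 9.3 with both parts of Section 10.1.2, and state which governs.

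Cost: a short text change under the procedure in Section 13.4, site guidance, and an eCRF field for elective CV admissions if none exists. There will be a few more records and possibly a less favourable event count. The wording will depart somewhat from the AE text that Amendment 3 aligned across the mavacamten program. Ascertainment will change during the study, so the report should give the date from which the clarified rule applied.
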